10.0 Reporting Requirements

A data safety monitoring board (DSMB) at MD Anderson will monitor the trial annually for safety.

Criteria for response and toxicity:

10.1 Adverse Event

Any unfavorable or unintended symptom, sign, or disease (including abnormal lab) temporally associated with the use of a medical treatment or procedure that may or may not be considered related to the medical treatment or procedure. Such effects can be intervention related, dose related, route related, participant related, and caused by an interaction with another drug.

10.2 Serious Adverse Event

Any adverse drug experience occurring at any dose that results in any of the following outcomes:

- Death
- A life-threatening adverse drug experience – any adverse experience that places the participant, in the view of the initial reporter, at immediate risk of death from the adverse experience as it occurred. It does not include an adverse experience that, had it occurred in a more severe form, might have caused death.
- Inpatient hospitalization or prolongation of existing hospitalization
- A persistent or significant disability/incapacity – a substantial disruption of a person's ability to conduct normal life functions.
- A congenital anomaly/birth defect.

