5.3.1 Endometrial biopsy

An endometrial pipelle biopsy will be performed at the Screening Visit 2 and at the 4th month on days 115-125 (plus or minus 10 days) into treatment in all participants from (all four arms) both groups.

In addition to histologic examination, each endometrial biopsy will be examined for proliferation markers as well as other biomarkers. The second biopsy in the no treatment group is important in order to determine variability in the biomarkers due to sampling. In preliminary data from the Wyeth-Ayerst Study, we did see variability in certain transcript levels at the 3 and 6 month time points even in the placebo control group. Therefore, we feel strongly in this study that women in both groups undergo a 4 month EMB.

Risks of office endometrial biopsy are small, and while there are no published data on risk of perforation, we believe that the risk is less than 1/1000. Even in those participants in whom uterine perforation occurs, observation alone is usually sufficient. The severe perforations requiring laparotomy and emergent hysterectomy are not seen in office endometrial biopsies, rather in Dilatation and Curettage (D & C) procedures performed in the operating room.

Participants who have no allergies will be instructed to take orally Non- Steroidal Anti-inflammatory Drugs (NSAIDs) before and after the biopsies to reduce pain and cramping. The NSAIDs medications are available over the counter (See Section 5.2 for the recommended dose).

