6.2 Lifestyle Intervention

The lifestyle intervention will use the 4 month intervention developed for the Diabetes Prevention Trial (DPT). This intervention has been found to be feasible, result in weight loss and prevention of diabetes, and produce changes in diet and physical activity. The goals of the intervention are for the participants to lose 7% of their body weight, decrease fat consumption, and increase their energy expenditure by 700

kilocalories per week (equivalent to approximately 2.5 hours per week of moderate intensity walking). Participants can choose whether they want to start with dietary or activity changes first (see Table 3 for schedule of topics), but both goal areas will be addressed.

Strategies to encourage weight loss include self-monitoring of weight and reduction of fat intake (goal: approximately 25% of calories from fat). Individuals who are not able to lose weight with these two strategies will be given a calorie goal during the seventh or eighth week of the intervention sessions in the session titled "Tip the Calorie Balance". Strategies to increase physical activity include self-monitoring, use of a pedometer to increase activity, and provision of opportunities for exercise.

The intervention is delivered as a 16 in-person sessions offered over a 4 month period, once each week. If a participant is travelling when a session is scheduled, or has some other reason why she is not able to attend, the session can be done by telephone. Participants will receive print material, worksheets, measuring utensils, a food scale, and a pedometer.

All print materials have been developed by the DPT and are available for use; they will require only minor modifications for this study. Print material and worksheets to be given to participants are provided in Appendix G. The intervention also involves providing opportunities for supervised exercise (e.g., group exercise class, group walks) at least twice a week for participants. The 16 interventions sessions will be delivered by a master's level Research Coordinator or Research Dietician who will be trained in a manner consistent with the requirements of the DPT. For quality control, 10% of the sessions he/she conducts will be audio-recorded and reviewed by [name] or a Senior Research Coordinator or Research Manager.

Table 3: Schedule of intervention sessions.

	Session
1	Welcome to the Group Lifestyle Balance Program
2	Be a Fat and Calorie Detective
3	Healthy Eating
4	Move Those Muscles

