6.4 Toxicity assessment

The summary of toxicity assessment for in-person and phone is listed below.

A. In-person assessment include:

- physical exam (only on 1st month)
- weight
- review of study medication side effects (as listed in consent and instruct participant to call if they experience symptoms of abdominal pain, anorexia, nausea, jaundice, and change in urine color)
- ALT and creatinine levels.
- Dispense Pill Diary and prescription.

B. Phone assessment include reported symptoms of:

- gastrointestinal (abdominal pain and severe diarrhea)
- liver (jaundice) and review ALT lab results
- kidney (changes in urine color and amount) and review creatinine lab results
- heart (CHF)
- rare side effects listed in consent

The in-person toxicity assessment will be at the end of each month and will be a month from Randomization / Visit 3. All participants must agree to keep a drug administration diary (Pill Diary). This diary will be signed by both the participant and research nurse and reviewed during each clinic visit to verify compliance. The medication administration record will be filed in the participant's chart. Any discrepancies will be noted along with

the reason, if known. Any remaining pills will also be returned at each clinic visit and documented.

Participants with mild elevations in ALT (3x ULN), will continue study drug at same dose, and have another ALT drawn 30 days later. If ALT levels are \geq 4x ULN, the study drug will be stopped, and participant removed from the study. Participants with an elevation in creatinine of \geq 2.5x ULN will be taken off of the drug and removed from the study. The study drug will be stopped and participant removed from study if the participant reports symptoms of congestive heart failure (CHF) such as: fatigue, tightness or congestion in the chest, edema to ankles or lower extremities, and shortness of breath.

Telephone contacts will be made periodically as needed to assess on the first, second, third, and fourth month (plus or minus 10 days) to encourage compliance and assess for the presence of toxic or adverse effects. Participants experiencing toxic or adverse effects will be referred to MD Anderson health providers for medical care however medical care will be billed to the participant or participant's insurance provider. All participants will be contacted by telephone 4 weeks after completion of the study for follow-up and toxicity assessment.

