9.0 Statistical Considerations

This is a partially blinded, randomized study to evaluate the effects of intervention upon Ki-67 and other biomarkers. Participants and researchers will be blinded with regard to assignment of study drug (placebo vs. metformin) but they will not be blinded with regard to assignment of lifestyle intervention. We will use a form of adaptive randomization called minimization, which is similar to stratification in that participant characteristics are used to assign them to the treatment conditions to achieve better group balance. Groups will be balanced with regard to age (50-65 years), BMI (Class I and II: 30.0-39.9 and Class III or greater: ≥ 40), and whether they meet current exercise guidelines as recommended by the Physical Activity Guidelines for Americans.

The primary objective of this study is to evaluate the effect of intervention (metformin and/or lifestyle intervention) on Ki-67. Secondary endpoints include examination of intervention on:

- (a) genes relevant to estrogen dependent endometrial proliferation, hyperplasia and cancer using Q-PCR (PCNA, sFRP4, RALDH2, IGF-1R, survivin, and EIG121),
- (b) biomarkers specific to the effect of metformin treatment (phospho-AMPKa, phospho-ACC, phospho-mTOR and phospho-S6 ribosomal protein).

Additionally, we will examine changes in serum levels of estradiol, estrone, testosterone, DHEA-S, sex hormone binding globulin (SHBG), adiponectin, glucose,

HbA1c, insulin and insulin-like growth factor-1 (IGF-1) and all biobehavioral outcomes, such as changes in body composition, physical activity, quality of life (QoL), diet, etc.

We will analyze differences in Ki-67 and other outcomes using 2x2 ANOVA models. If lifestyle intervention is found to affect change in Ki-67 expression or other outcomes, we will use the methods described by Baron and Kenney [78] to determine whether these changes were mediated by weight loss, body composition changes, physical activity changes, and dietary changes. Differences between arms with regard to adverse events and other toxicities will be examined using Fisher's exact tests. Changes from baseline lab values will be examined 2x2 ANOVA models.

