10.3 Eliciting Adverse Event Information

Adverse events will be elicited at each clinic visit during participation in the study. Participants will be given frequent toxicity screening (in-person and phone) to review the occurrence of adverse events monthly and throughout the study. All adverse events which are directly observed and all adverse events which are spontaneously reported by the participant are to be documented by the investigator.

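### The serious adverse event definition covers only drug experiences, so serious harm from supervised exercise or from the biopsy falls outside it as written

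*Combined protocol and SAP*

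**What the plan says.** Section 10.1 defines an adverse event as something "temporally associated with the use of a medical treatment or procedure that may or may not be considered related to the medical treatment or procedure", and adds: "Such effects can be intervention related, dose related, route related, participant related, and caused by an interaction with another drug". Section 10.2 then defines a serious adverse event as "Any adverse drug experience occurring at any dose that results in any of the following outcomes", followed by the usual outcome criteria (death, life-threatening, hospitalization, disability, congenital anomaly).

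Section 10.3 has adverse events elicited at each clinic visit and requires that those directly observed and "all adverse events which are spontaneously reported by the participant are to be documented by the investigator". Section 10.4 grades every reported event. Section 10.6 rates relationship to study treatment as a single item.

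The in-person assessment in 6.4 includes "review of study medication side effects". The telephone list in 6.4 names gastrointestinal, liver, kidney and heart symptoms and the rare effects listed in the consent form.

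On exposure, 5.4 gives every arm four monthly in-person toxicity visits. Under 6.2, "The intervention is delivered as a 16 in-person sessions offered over a 4 month period, once each week", with supervised exercise offered at least twice a week. Section 5.3.1 schedules a biopsy at Screening Visit 2 and another at month 4 in all arms, and says of perforation that "we believe that the risk is less than 1/1000". On analysis, 9.0 states: "Differences between arms with regard to adverse events and other toxicities will be examined", using Fisher's exact tests.

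**The concern.** There are two issues.

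**Classification.** The drug is only one of the things done to these women. The lifestyle program is the second randomised factor, and the biopsies are study procedures. A seriousness definition tied to a drug experience does not naturally reach harm from either. The consequence would be a serious-event tabulation that under-represents one randomised intervention and the main study procedure.

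**Comparability.** Section 9.0 compares adverse events between arms without saying how the compared events were obtained. Staff see lifestyle participants far more often, and that assignment is unblinded. If volunteered events count equally, the chance that an event becomes known may differ between lifestyle and no lifestyle even when true incidence does not. The metformin contrast is largely protected: drug assignment is blinded and the extra contacts fall equally on both sides of it.

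**Working it through.** **1. The definitions side by side**

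| Event | Adverse event under 10.1? | Recorded and graded (10.3–10.5)? | Serious under the words of 10.2? |
|---|---|---|---|
| Hospitalization attributed to study drug | Yes | Yes | Yes |
| Hospitalization after injury at a supervised exercise session | Yes, if the program is read as a treatment (10.1 mentions intervention-related effects) | Yes | Not if it is judged unrelated to the drug |
| Hospitalization after the month-4 biopsy | Yes (procedure) | Yes | Not if it is judged unrelated to the drug |
| Hospitalization after the baseline biopsy | Yes (procedure) | Yes | No: no capsule has been taken |

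The last row is the clearest. The baseline biopsy is at Screening Visit 2 (5.3.1), while randomization and the first prescription come at Visit 3 (5.4). No complication of that biopsy before Visit 3 can be a drug experience on any reading. In the two middle rows, seriousness depends on a causality judgement, which 10.1 deliberately avoids.

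**2. Biopsy exposure**

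Inputs: 100 randomised women with two biopsies each, and the protocol's stated ceiling of 1/1000 for perforation.

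- At least one perforation in 200 biopsies: 1 − 0.999^200 = 18.1% at most.
- At least one in the 100 baseline biopsies: 1 − 0.999^100 = 9.5% at most.

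These are ceilings for any perforation. Section 5.3.1 says observation alone is usually enough, so the chance of a serious one is lower.

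**3. Checklists**

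The items visible in 6.4 are framed around the drug. Abdominal pain is on the list and could bring a biopsy complication to light incidentally. No visible item asks about exercise injury or about the biopsy. Items carried in the consent form cannot be seen.

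**4. Contacts over four months**

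- No lifestyle: 4 scheduled in-person visits. Lifestyle: 4 + 16 = 20, a ratio of 5.
- Counting one as-needed telephone contact a month in every arm: 8 against 24, a ratio of 3.
- If every optional exercise session were attended (2 × 16 = 32): 52 against 4. This is an upper extreme.

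**5. What unequal capture could do**

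The plan gives no adverse-event rate, so there is no figure to reproduce. As an illustration, assume the same true incidence in both lifestyle groups, 50 against 50, and a two-sided 5% Fisher test. Observed rate = true incidence × capture. Rejection rates come from summing exact binomial probabilities over all tables.

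| True incidence (assumed) | Capture 70% v 70% | 70% v 90% | 50% v 80% |
|---|---|---|---|
| 10% | 1.3% | 2.1% | 2.8% |
| 20% | 2.3% | 4.7% | 8.0% |
| 30% | 2.9% | 7.2% | 14.3% |
| 60% | 3.3% | 18.3% | 38.3% |

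For example, 60% incidence with 70% v 90% capture gives observed rates of 42% v 54%. For individual event types at 10% incidence, even the widest capture gap shown stays below the nominal 5%. For a common composite such as any adverse event, the inflation can be material.

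**The case against.** The best defence is that nothing goes unrecorded. Section 10.1 already covers procedures and intervention-related effects, 10.3 captures all observed and volunteered events, and 10.4 and 10.5 grade them up to life-threatening and fatal. Section 10.0 has the monitoring board review safety annually and does not confine it to serious events. The explanatory text of the life-threatening criterion in 10.2 also speaks of an adverse experience without the word drug. All of this stands except the last item, which carries little weight because that criterion itself opens with the drug-specific term. A reader might infer that lifestyle and biopsy harms are generally misclassified or hidden from the board. The documents do not support that; the literal gap is the serious label.

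A reader might also infer that the lifestyle comparison is biased towards excess harm. That is not established either. The scheduled toxicity visits are identical in all arms. No text calls lifestyle sessions clinic visits or makes them a collection point for adverse events. Direction is open as well: extra contact could inflate lifestyle events, while prompts centred on the drug could miss them. Biopsies are done in all four arms, so their omission from 10.2 does not by itself bias the lifestyle contrast.

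Finally, it is tempting to confine the Fisher comparison to events elicited at the common visits. As the main analysis this could drop exercise injuries first reported at sessions, which are harms the trial needs to count. That objection stands, and it is why such a restriction belongs only in a sensitivity analysis.

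**Conclusion.** The wording inconsistency is real and rests on the text alone: 10.2 is narrower than 10.1 and leaves out serious harm from the lifestyle program and the biopsies when it is not attributed to the drug. The baseline biopsy is unambiguous. The number of affected events is probably small: at most an 18.1% chance of any perforation across 200 biopsies, few of which would be serious. The documents give no rate for exercise injury.

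Detection bias in the lifestyle adverse-event comparison is a risk the plan does not control, of unknown size and direction. The 2.1% to 38.3% range under unequal capture depends on assumed incidence (10% to 60%) and assumed capture rates. The 18.3% and 38.3% values require a 60% incidence that appears nowhere in the plan. The statement about checklists is limited to the items visible in 6.4. The change is worth making because it improves safety classification at almost no cost.

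**What to change.** - **10.2:** replace the term adverse drug experience, in the opening line and in the life-threatening criterion, with adverse event as defined in 10.1, whatever the cause.
- **10.1:** state that the definition includes events associated with study drug, the lifestyle intervention or a study procedure.
- **6.4 and 10.3:** at the four common monthly visits, ask the same neutral open question in all arms, plus items on exercise injury and biopsy complications. Because the second biopsy falls at about the month-4 visit, repeat the biopsy item at the existing four-week telephone follow-up.
- **Adverse-event form:** add a field for how each event came to light (common visit, telephone call, lifestyle or exercise session, other).
- **9.0:** keep the Fisher comparison of all events. Add a sensitivity comparison limited to events elicited at the common visits, with serious events from any source counted in both.

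The cost is a protocol wording change, a few checklist items, one form field and one extra table.

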10.3 Eliciting Adverse Event Information

Adverse events will be elicited at each clinic visit during participation in the study. Participants will be given frequent toxicity screening (in-person and phone) to review the occurrence of adverse events monthly and throughout the study. All adverse events which are directly observed and all adverse events which are spontaneously reported by the participant are to be documented by the investigator.

10.4 Grading/Rating Scale

All adverse events reported during the study will be evaluated and graded on a scale of 0-5. The CTCAE version 4.0 will be used to determine the grade for all toxicities. For any adverse events which are not listed in the CTCAE version 4.0 the following rating system will be used as listed below in section 10.5.

10.5 Non-NCI Adverse Event Grading Scale Grade/Description

- 0 No adverse event (absent) or within normal limits
- 1 Mild adverse event (minor, no specific medical intervention, asymptomatic laboratory

findings only, radiographic findings only, marginal clinical relevance)

- 2 Moderate adverse event (minimal intervention, local intervention, non-invasive intervention [packing, cautery])
- 3 Severe and undesirable adverse event (significant symptoms requiring hospitalization or invasive intervention; transfusion; elective interventional radiological procedure; therapeutic endoscopy or operation)
- 4 Life threatening or disabling adverse event (complicated by acute, life threatening metabolic or cardiovascular complications such as circulatory failure, hemorrhage, sepsis. Life-threatening physiologic consequences; need for intensive care or emergent invasive procedure; emergent interventional radiological procedure therapeutic endoscopy or operation)
- 5 Death related to adverse event

10.6 Relationship to Study Treatment

The investigator will use the following definitions to assess the relationship of the adverse event to the study treatment:

- Definite: Adverse event is clearly related to the study treatment.
- Probable: Adverse event is likely related to the study treatment.
- Possible: Adverse event may be related to the study treatment.
- Unlikely: Adverse event is doubtfully related to the study treatment.
- Not Related: Adverse event is clearly not related to the study treatment.

11.0 Laboratory Evaluations and Procedures

11.1 Laboratories

- 11.1.1 Serum assays will be performed at the MD Anderson Cancer Center Clinical Laboratory (estradiol, estrone, testosterone, DHEA-S, SHBG, adiponectin, glucose, hemoglobin, FSH, A1c, insulin and IGF-1).
- 11.1.2 The endometrial biopsy slides will be reviewed centrally by the study's co-PI, [name]., Ph.D. at MD Anderson Cancer Center and PI of the Pathology core. A pathology report will be generated and forwarded to the participant's study gynecologist.

Cases with hyperplasia or adenocarcinoma will be confirmed by a second review by [name]., a senior gynecological pathologist at MDACC. [name] is a Professor with more than 25 years of experience and is regarded as an international expert in gynecologic pathology.

- 11.1.3 Ki-67 immunohistochemical assays, as well as IHC for metformin associated

phosphoproteins, will be performed in the Histology Core Lab at MD Anderson.

11.1.4 Q-PCR for estrogen-regulated genes will be performed in the laboratory of [name]., U.T. -Houston Medical School (Biomarkers core).

11.2 Collection and Handling Procedures

An endometrial biopsy using 4 mm pipelle will be used to obtain endometrial tissue. Half of the sample will be placed in formalin, and half of the sample will be placed in a cryovial and immediately snap frozen in liquid nitrogen. The sample in formalin will undergo routine histological-processing and paraffin-embedding. One H&E slide will be cut per block. Following central pathologic review, the pathology report will be forwarded to the participant's study gynecologist.

11.3 Shipping Instructions

Snap frozen tissue will be batched and shipped periodically on dry ice to [name] at the University of Texas - Houston Medical School, PI of the Biomarkers Core.

Snap frozen tumor will be shipped in liquid nitrogen to M. D. Anderson Gynecologic Oncology Translational Research Tumor Bank.

